MeHg impact on human health. Exposure to MeHg through consumption of fish continues to pose a health risk for many populations globally. The developing nervous system is a preferred target for MeHg toxicity, making the fetus and young children most vulnerable. Conflicting results from large epidemiological studies has lead to uncertainty in advising the public on mercury risks associated with fish consumption [1-3]. At odds are the potential harmful effects of Me Hg and the beneficial effects of dietary nutrients and antioxidants in fish. A great deal of uncertainty for this conflict stems from the fact that MeHg metabolism and elimination rate is known to vary widely from individual to individual. This translates into the possibility that two individuals consuming the same amount of fish with the same frequency could, unknowingly, experience as much as 4-fold difference in MeHg in their bodies. Thus, there is a need for greater understanding of the mechanisms of MeHg metabolism and elimination, as well as for development of tools to assess these characteristics in people.

MeHg toxicokinetics: the importance of elimination rate. Orally ingested MeHg is absorbed very efficiently in the intestine with 95% of the dose typically being taken up and distributed to the bloodstream [4]. MeHg undergoes rapid transport and equilibration between blood and target organs [4]. Subsequent to an initial "spike" in concentration, mercury levels in blood resolve to a slow steady rate of decline that is dictated by the overall elimination rate of Me Hg from the body [4-6]. Elimination rates,

expressed as half time ($t_{1/2}$), range from <30 to >120 days, demonstrating the existence of “fast” and “slow” MeHg metabolizers [4-11]. The elimination rate of MeHg is a major determinant for accumulation of MeHg to the elevated steady state levels that occur in people who consume fish on a regular (e.g. weekly or daily) basis. The ability to determine the MeHg metabolism and elimination status of an individual is therefore a means of prospectively identifying “fast” versus “slow” metabolizers.

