- Subjects must be in good general health based on self-reported health status, with the exception of self-reported conditions listed in the exclusion criteria.
- Subject must be willing to comply with study procedures.

Exclusion Criteria:

- Known allergy to fish.
- Pregnant or lactating women.
- Use of hair dyes or chemical treatments within the prior month and/or intent to use such treatments during the two trial periods. (Hair treatment during the washout period up to one month prior to the second trial is acceptable).
- Known gastrointestinal or renal disorders.
- Subjects with diminished mental capacity.
- Use of antibiotics within two months leading up to the study.

3C. Discussion of Subject Population

The inclusion criteria are very broad and it is anticipated a large diversity in age and ethnicity will result. This is acceptable as age and ethnicity, although not primary study objectives in this pilot, are likely to produce variation in MeHg metabolism and elimination status, the determination of which is an objective of the study. Exclusion criteria are defined based on factors that are likely to result in either harm to the subject or to substantially alter the metabolic processes or analytical procedures of MeHg and thus obscure results. Of particular concern is exposure to the fetus or infant to MeHg, which is known to target the developing nervous system. This concern warrants exclusion of pregnant or breast-feeding women.

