4. SUBJECT IDENTIFICATION, RECRUITMENT, CONSENT AND COMMUNICATION

4A. Method of Subject Identification and Recruitment

Subjects will be recruited through local advertising by posting RSRB-approved flyers around the University of Rochester Medical Center. Response via phone and email to these postings will be anticipated. The P.I. and Lab personnel will also inform friends and acquaintances about the study. Lab personnel will be prepared to tell interested persons of the existence of the study and provide interested persons with contact information for the P.I. for follow up. The Lab personnel will not inquire about health status or other personal information required of interested persons for consent. For phone inquiries the P.I. will perform an initial screening. Potential subjects will be asked if any of the following apply to them:

- Do you have any known allergy to fish?
- Are you pregnant or currently breastfeeding?
- Have you used hair dyes or treatments within the last month?
- Do you have any gastrointestinal or renal (kidney) disorders?
- Have you used antibiotics within the last month?

Subjects answering "no" to all of the above will be asked to follow up with the initial office visit.

Process of Consent

Subjects with Capacity: Only subjects with capacity will be recruited into the study. Subjects with capacity will be consented by the P.I. or study coordinator (TBD) listed on the protocol. The consent form will be reviewed with the subject directly, and the subject will also be offered the opportunity to review the consent form on their own. They will be encouraged to ask any questions and will be free to choose whether or not to participate.

Subject Comprehension: All subjects will be asked, in a private setting, if they understand all aspects of the consent form and expectations of participation in the protocol. They will be provided with contact information for the investigator and encouraged to ask for clarification at any time. Reading skills will be assessed by asking all participants, in private, if they would like any assistance in reading forms.

Documentation of Consent. All subjects will receive a signed copy of the consent form, and all consent forms will be kept on file in a locked office [name].

Costs to Subjects. There will be no costs incurred by subjects participating in the study.

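### Pregnancy eligibility looks only at current status, checked once before Trial 1, although study methylmercury persists for months: a bounded gap in eligibility and monitoring

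*Combined protocol and SAP*

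**What the plan says.** - **Criterion (3B).** The exclusion is "Pregnant or lactating women". It does not mention planned pregnancy.
- **Phone screen (4A).** The question is "Are you pregnant or currently breastfeeding", which again concerns the day it is asked.
- **Reason (3C, 9A).** 3C states: "Of particular concern is exposure to the fetus or infant to MeHg, which is known to target the developing nervous system". 9A gives the risk to the developing nervous system as the ground for leaving out pregnant and breast-feeding women.
- **Persistence (1C).** Elimination half-times "range from <30 to >120 days".
- **Timing (5C, Appendix 1).** Each trial has meals on days 0, 7 and 14 and ends near day 74. Two trials are separated by a 4-month washout. Eligibility has one mark in Appendix 1, before day 0 of Trial 1. A visit does take place before Trial 2 (5A; food diary paragraph of 5C), where fish intake, illness and stress are asked about, but not pregnancy.
- **Safety (Sections 7 and 8).** Neither mentions a pregnancy that begins on study.
- **Population (3A).** 23 women are to be consented, aged 18 to 80.
- **Exposure cap (5C, 9A, 9B).** The fish is assayed first, and portions are sized by body weight so that blood MeHg stays at or below the RfD level of 5.8 µg/L, which includes a safety factor of 10.

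**The concern.** The protocol ranks fetal exposure first among its reasons for exclusion, but asks only about status on one day before the first trial. The exposure lasts much longer than that day. There are three meals, a 60-day elimination phase that depends on mercury still being present, a washout, and then three more meals. A woman who says at screening that she plans to conceive next month meets every written criterion and could conceive while carrying study mercury. A woman who conceives during the washout is not asked again before the Trial 2 meals.

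The same list shows that a forward-looking criterion is workable here: the hair-treatment exclusion extends to "intent to use such treatments during the two trial periods". At stake is a safety protection. Sample size, power and analysis are unaffected.

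**Working it through.** **1. The plan's own dose figures (9B).**
- Single dose giving 5.8 µg/L: 5.8 × 4.2 / 0.059 = 412.9 µg and 5.8 × 6.5 / 0.059 = 639.0 µg. The plan states 413-639 µg.
- Three 8-oz portions at 0.39 ppm: 3 × 227 × 0.39 = 265.6 µg. The plan states 265.5 µg.

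Both reproduce.

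**2. Persistence.** Assume one compartment with first-order decay. The share of one trial's cumulative dose left at day t, for half-time h, is the mean of 2^(−(t − a)/h) over a = 0, 7, 14.

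| Day | h = 30 | h = 120 |
|---|---|---|
| 14 (last meal) | (0.724 + 0.851 + 1)/3 = 0.858 | (0.922 + 0.960 + 1)/3 = 0.961 |
| 74 (hair visit) | (0.181 + 0.213 + 0.250)/3 = 0.215 | (0.652 + 0.679 + 0.707)/3 = 0.679 |
| 194 (Trial 2 day 0) | 0.013 | 0.340 |

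Day 194 is 74 + 120, taking four months as 120 days. The values 30 and 120 are not limits, because 1C says that half-times fall below the one and above the other.

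At day 74 of Trial 2, adding the Trial 1 remainder gives 0.217 (h = 30) and 0.901 (h = 120) of one trial's dose. Study mercury therefore outlasts the final visit as well.

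**3. Size in blood.** Use 9B's 5.9% of dose in blood, 4.2 L (a 130-pound person, the lightest in 9B's example) and 265.5 µg. Before decay this is 265.5 × 0.059 / 4.2 = 3.73 µg/L.
- Day 14: 3.73 × 0.858 = 3.2 and 3.73 × 0.961 = 3.6 µg/L.
- Day 74: 3.73 × 0.215 = 0.8 and 3.73 × 0.679 = 2.5 µg/L.
- Day 14 of Trial 2 at h = 120, with Trial 1 carry-over: 3.73 × (0.961 + 0.340 × 0.922) = 4.8 µg/L.

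All are below 5.8 µg/L. They are study-derived levels at average tuna content and include no mercury from other fish.

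**4. The criteria against the timeline.** For a woman who plans to conceive during the study, the documents offer three places where this could surface. The 3B criterion and the 4A question do not ask about it, and the visit before Trial 2 is not stated to ask about pregnancy. Section 8 does not name pregnancy as something to report.

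**The case against.** The strongest reply is the exposure cap. Fish is assayed, portions are sized to body weight, and the RfD level carries a tenfold safety factor. Step 3 bears this out at average tuna content. This stands as a limit on the size of the exposure, but it does not close the gap, because the protocol excludes pregnant women despite the cap. The 9B calculation also covers one trial's meals only, with no term for carry-over or for other fish, which 2A permits during washout.

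A second reply is that 3B does what 3C concludes. From the fetal concern, 3C draws the exclusion of pregnant and breast-feeding women, and 3B excludes them. That is correct. A reader might infer that the criterion contradicts its stated purpose, but the documents do not support that. The criterion is narrower than the concern and the half-times would suggest.

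Third, the hair criterion is an imperfect comparison. It protects an assay, it allows treatment during the washout, and the matching 4A hair question looks only backwards. It shows that asking about intent is feasible here, but its wording should not be copied, because the washout matters for mercury.

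Fourth, the consent form is not in the text reviewed and may carry a warning about conception. A reader might infer that women go unwarned; that cannot be concluded. A warning would still leave the 3B criterion and the 4A question unchanged.

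Finally, the documents do not say how many of the 23 women might plan a pregnancy, so the frequency is unknown.

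**Conclusion.** The point holds as a gap in eligibility and monitoring. Current status, asked once before Trial 1, is the only written check on pregnancy. On the protocol's own half-times, about 21-68% of a trial's meal dose remains at day 74 and about 1-34% at the start of Trial 2. A woman planning to conceive is eligible as the criteria are written.

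It is tempting to go further and say that the study would expose a fetus to a harmful dose. The documents do not support that. At average tuna content, the study-derived blood level is about 3.2-3.6 µg/L at day 14 and 0.8-2.5 µg/L at day 74, against an RfD level of 5.8 µg/L, and portions are to be adjusted for fish with more mercury.

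The figures assume one-compartment decay, half-times of 30 and 120 days, a 120-day washout, 265.5 µg per trial and 4.2 L of blood. A longer half-time would raise the remaining shares. The conclusion about eligibility depends only on the text of the criteria.

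**What to change.** Reconcile 3B, 4A, Section 8 and Appendix 1 with the fetal concern in 3C and 9A and the half-times in 1C:

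- Extend the 3B criterion and the 4A question to intent to become pregnant during the study, including the washout, and for a period after the last meal. The investigator and the RSRB should set that period from the protocol's own half-times. Wording limited to the two trial periods would leave out the washout and the months after Trial 2, which the persistence figures also concern.
- Repeat the pregnancy question at the existing visit before Trial 2, and mark it in Appendix 1.
- List pregnancy in Section 8 among the events that subjects report to the investigator. A question about intent cannot catch an unplanned conception, and this item at least makes it known. Any action after a report stays with the investigator and the RSRB.
- Check that the consent form agrees with the revised criterion.

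The cost is a few words in each place, one question at a visit that already takes place, and a slightly smaller pool of eligible women for the target of 23. Sample size and analysis do not change.

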4. SUBJECT IDENTIFICATION, RECRUITMENT, CONSENT AND COMMUNICATION

4A. Method of Subject Identification and Recruitment

Subjects will be recruited through local advertising by posting RSRB-approved flyers around the University of Rochester Medical Center. Response via phone and email to these postings will be anticipated. The P.I. and Lab personnel will also inform friends and acquaintances about the study. Lab personnel will be prepared to tell interested persons of the existence of the study and provide interested persons with contact information for the P.I. for follow up. The Lab personnel will not inquire about health status or other personal information required of interested persons for consent. For phone inquiries the P.I. will perform an initial screening. Potential subjects will be asked if any of the following apply to them:

- Do you have any known allergy to fish?
- Are you pregnant or currently breastfeeding?
- Have you used hair dyes or treatments within the last month?
- Do you have any gastrointestinal or renal (kidney) disorders?
- Have you used antibiotics within the last month?

Subjects answering "no" to all of the above will be asked to follow up with the initial office visit.

Process of Consent

Subjects with Capacity: Only subjects with capacity will be recruited into the study. Subjects with capacity will be consented by the P.I. or study coordinator (TBD) listed on the protocol. The consent form will be reviewed with the subject directly, and the subject will also be offered the opportunity to review the consent form on their own. They will be encouraged to ask any questions and will be free to choose whether or not to participate.

Subject Comprehension: All subjects will be asked, in a private setting, if they understand all aspects of the consent form and expectations of participation in the protocol. They will be provided with contact information for the investigator and encouraged to ask for clarification at any time. Reading skills will be assessed by asking all participants, in private, if they would like any assistance in reading forms.

Documentation of Consent. All subjects will receive a signed copy of the consent form, and all consent forms will be kept on file in a locked office [name].

Costs to Subjects. There will be no costs incurred by subjects participating in the study.

Payment for Participation. Subjects will be reimbursed with “rewards cards” from Wegman’s Supermarket. Renumeration will be prorated such that participants will receive \$25 upon completion of trial 1 and an additional \$50 (\$75 total renumeration) upon completion of trial 2.

Use of E-mail for Communication in Research

E-mail communication will be used in recruitment and in scheduling visits and follow ups. E-mail will not be used in screening or consenting of subjects. E-mail will also be a means for subjects to contact [name] with any study concerns. When using e-mail to communicate with subjects in this study, the researcher cannot guarantee, but will use reasonable means to maintain security and confidentiality of e-mail information sent and received. Minimizing the risks for this is described below (9A, B).

5. METHODS AND STUDY PROCEDURES

5A. Overview:

The study will follow the protocol outlined below under “specific methods”. A timeline of study activities can be seen in Figure 1 and Appendix 1. The study will engage human subjects in six activities to execute this protocol: 1) recruitment, 2) collection of body metrics (weight, height) and oral observation for presence/absence of amalgam fillings, 3) fish meal consumption 4) fecal sample collection and submission and 5) hair sample collection, 6) prebiotic self-administration (see below). A total of four visits will be mandatory, one at the beginning and one at the end of each trial. Fecal sample submission will be done with a shipping protocol, or scheduled pick up by lab staff, and will not require a visit. Steps 2-4 above are anticipated to occur over a period of approximately 74 days (see Figure 1 and Appendix 1). Step 5 will commence one week prior to the first fish meal in the second trial (Figure 1). Subjects will be asked to keep a food diary in a provided notebook and include notes on their general health, and particularly any illness or unusual diet habits, over the study period. The entire study, including pre-study preparations, subject enrollment, two trials of fish meal administration and hair and feces sampling, Hg measurements, microbiome analysis and statistical analysis of the data is anticipated to take place over a period of three years.

5B. Approach.

Our approach is summarized schematically in Figure 1. Subjects will consume three meals of tuna steaks, each meal separated by seven days (on days 0, 7 and 14”). This will be followed by an elimination period of 60 days where subjects will resume normal daily diets and activities. Hair will be sampled on or near the 60th day after the last fish meal. Fecal samples will be taken at three time points: one each within 30 days following the last fish meal for each trial and one prior to, or upon the day of initiating the prebiotic administration in the second trial. Longitudinal Hg analysis of single hair strands will be performed with LA-ICP-MS. iHg and MeHg levels will be determined in fecal samples using tetra-ethylborate (NaBEt₄) derivatization and GC-ICP-MS methods.

Fecal DNA will be extracted and stored frozen. Hair Hg analyses will give Hg levels over time and will be used to determine a MeHg elimination rate ($t_{1/2}$). Fecal Hg analyses will be used to determine iHg/MeHg ratio as a proxy of MeHg de-methylation, and adjusted based on presence of dental amalgam. Fecal samples and isolated DNA will be shipped to MSU for germ-free mouse microbiome experiments and metagenomic sequencing and bacterial culturing and abundance analyses. Statistical analyses of correlations of elimination rate, MeHg demethylation and bacterial taxa abundance will be made.

5C. Specific methods.

(Many of the specific methods below are reiterated from our previously approved project: RSRB00050613 entitled Methylmercury metabolism and elimination in humans and RSRB00057934 entitled Determination of methylmercury metabolism and elimination status in humans.)

Subject recruitment and subject information. Potential subjects responding to flyer announcements of the study will be scheduled for a confidential visit in the office of the Principal Investigator (P.I.) who will serve as the study leader. The study methods and objectives and subject responsibilities, risks and benefits will be explained to prospective participants. Willing participants will sign a consent form provided by the P.I. at the time of the first visit. Alternatively, potential subjects will be given the opportunity to take home a written description of the study for further consideration before consenting. The study will target 40 participants, 20 women and 20 men. To achieve this subject recruitment will target 46 consenting participants (23 women, 23 men) to account for attrition due to drop out. When 46 participants have signed a consent form recruitment will cease. Once consent is obtained the subject will be assigned an alpha-numerical identifier that will be used to label all associated samples, data and record keeping throughout the study. This identifier number will be recorded on the consent form and kept in a locked and secure file in the P.I.'s office.

Information collected from the subjects at the initial study visit will be: age, sex, body weight, presence/absence of dental amalgams and medications currently taken. This will be collected without the need to access medical records. Subjects will be provided with a notebook carrying templates to fill in for a food diary. Alternatively, subjects who currently use a personal food tracking application (e.g. "My Fitness Pal" or "Healthwatch 360") can substitute a print out from this application of their food consumption record for period spanning the trial.

Fish meal administration. Just prior to each trial, individually weighed, wrapped and frozen portions of tuna steaks in 6-8 oz (170-227gm) portions will be prepared by and purchased from a local market (Wegman's). Portions will be kept frozen in a dedicated freezer in the P.I.'s lab until the time of distribution to the subjects. Frozen fish portions will keep over the time of distribution to enrolling participants (~ 2-3 months, <https://stilltasty.com/fooditems/index/18559>). Tuna portions will be prepared from one large fish fillet, so subjects will be receiving portions from the same fish within each Trial. A sample of the fish tissue will be set aside at the time of purchase to determine mercury content in the fish. Mercury measurements will be performed at the URMC EHSC Elemental Analysis Facility. Fish mercury values will be used to calculate predicted exposures to subjects based on individual body weights (see 9B, Protection

against risks, below). Where needed, instruction for adjustment of the portion size will be made to assure that MeHg exposure levels will not exceed federal guidelines for each subject. Each subject will be provided with the three frozen portions of tuna in a Thermosafe styrofoam shipping container affixed with prepaid return postage for later return (see below). Two polar-pack freezer blocks will be included to maintain the frozen steaks during transport home. For safety, subjects will be instructed on the steps necessary to keep the fish frozen until preparation for eating. Since cooking does not affect MeHg content in fish, fish meals can be prepared to the subject's own liking and eaten at home. Suggestions for preparation of the fish will be provided to the subjects. Fish meals will be eaten on Days 0, 7 and 14. Subjects will record the date and time of consumption of each meal. Subjects will be instructed not to eat any fish or seafood during the 60 days following the final tuna fish meal. Subjects will be asked to keep a record of all types of food and drink consumed at each meal during the 60-day elimination period using a provided template or their personal food tracking application

Prebiotic administration. Prebiotin™ (oligosaccharide enriched inulin), a commercially available prebiotic supplement from Jackson GI Medical (<https://www.prebiotin.com/about-us/>), will be distributed to the subjects for self-administration subsequent to the first trial and washout period and prior to the second trial (Figure 1). An intended use for Prebiotin™ is not the subject of investigation in this study. Prebiotic supplementation with this lawfully marketed over-the-counter dietary supplement is being used for its known properties of changing gut microbiome composition. Regarding FDA approval, use of Prebiotin™ in this study will be IND exempt in that all six (6) of the conditions under section 7.1 of Policy 605 of the Office of Human Subject Protection at the Univ. of Rochester are met. Briefly, with respect to Prebiotin™, this study: is not intended to support a new indication for use (7.1.1); is not intended to support a significant change in the advertising of Prebiotin™ (7.1.2); does not involve a change in route of administration, dosage level, or population at risk (7.1.3); will be conducted in compliance with the IRB review (7.1.4); will be conducted in compliance with requirements concerning the promotion and sale of Prebiotin™ (7.1.5); and, does not intend to request exception from informed consent requirements for emergency use (7.1.6). Individually packaged portions (4 grams) of the Prebiotin™ Prebiotic Fiber Stick Pac will be provided to subjects (<https://prebiotin.net/collections/our-products/products/prebiotin-prebiotic-fiber-stick-pac-4g>). Prebiotin™ is the prebiotic of choice in several published studies on gut microbiota control of obesity [20-22] and has been used in an NIH study on reducing inflammation in kidney patients [23]. For this study, we are targeting a dose of 8 grams/day. This dose amount is based on published effects of inulin on gut microbiota in the range of 4 to 16grams/day dosages [20, 24]. We have selected 8 grams/day based on the finding of Holscher et al [24], who demonstrated clear effects on shifting the microbiota composition and activity at the 7.5 gram/day dose level in healthy adults in a controlled double-blinded study. Prebiotin™ self-administration will be initiated one week prior to fish consumption in the second trial and extend through the entirety of the second trial (i.e. 11 weeks, Figure 1). Subjects will be given a 11-week supply of Prebiotin™ Stick Pacs and instructed on how to self-administer on either a once or twice daily dosing schedule. For the first week, subjects will be instructed to begin with a daily supplement of one Pac (4grams) a day, taken with meals. Starting the second week, and additional

Pac (2 Pacs total) will be consumed to achieve 8 grams/day. Both Pacs can be consumed at breakfast, or alternatively, divided between meals, e.g. breakfast and dinner. Prebiotin™ has a mild natural sweetness and will dissolve readily in any liquid. It can also be added to any food such as cereal, soups, salads, or sauces. If disruptive bloating or gas occurs with the 8gram dose, then the amount can be reduced to one pouch (4grams/day) until bloating and/or gas is manageable. While Prebiotin is safe to use in very high quantities, subjects will be advised on what to expect with prebiotic ingestion, including the anticipated digestive health benefits as well as possible feelings of bloating and excess flatulence that are harmless yet may produce some annoyance. Where bloating or gas is not manageable/tolerable and is disruptive to daily life, participants will be advised to contact study staff for further recommendations on reducing supplementation amounts to 2 grams/day or pursuing the option to withdraw from the study.

Fecal sample collection, DNA isolation and shipping. Feces will be used to capture the profile of the gut microbiota for each subject. Collection methods will therefore be aimed at capturing and preserving anaerobic species. At the initial visit, subjects will also be provided with instructions on the stool sampling protocol and provided with an easy to use commercially available collection container (Fisherbrand Commode Specimen Collection System) and an Omnipore-Gut collection tube for DNA subsampling (below). Stools will be sampled at three time points as indicated in Figure 1: approximately four weeks after the 3rd fish meal (for each trial) and at approximately one week prior to the 2nd Trial, preceding or contemporaneously with prebiotic supplementation (e.g. day 44 of the Trial 1 and day -7 and 44 of Trial 2). Collection of stools within 2-3 days centered on these target collection times will be acceptable. For all fecal samplings, the whole stool will be collected and frozen within 30 minutes to preserve microbe viability [25]. To stabilize a sample of the fecal DNA at the time of stool collection, a sub-sampling of feces with the Omnipore-Gut collection kit (DNA Genotek, Ottawa, ON, Canada) will be done by the subject according to the provided instructions. Subjects will be instructed to triple contain the stool collection with freezer-grade zip-lock bags provided. Subjects will ship the stool sample and the DNA stabilized sample to the P.I.'s lab using express shipping (FedEx) as soon as possible using the freezer packs and Thermosafe styrofoam packaging provided (see above). Alternatively, sample pick up by lab staff will be arranged. Fecal samples will be logged-in and coded for identity protection in the P.I.'s laboratory and kept frozen until analysis and DNA isolation. Fecal DNA will be isolated with the ZR fecal prep kit (Zymo Research) in the [name] lab and will be distributed to the [name] lab at MSU. Samples of feces will also be distributed to the [name] lab at MSU. Human feces falls under the "exempt human/animal specimens" category for shipping. A portion of frozen stool for each subject will be prepared in appropriate triple-layer packaging and containment (http://www.fedex.com/us/packaging/guides/Clinical_fxcom.pdf) and marked appropriately with "exempt human specimens" for shipping to MSU.

Hair sample collection and submission. Hair samples will be collected during a visit of the subject to the P.I.'s laboratory on approximately day 74 (60 days after the last fish meal). Sampling within a five-day window of this target time will be acceptable. Hair will be sampled manually by direct withdrawal from the scalp. Sampling from the posterior region of the head will be done for all the subjects. Direct withdrawal of three

to five strands at once is found to elicit little discomfort and yield root material that can be used as a reference landmark for the start of the LA-ICP-MS analysis. A total of 20-25 hair strands will be collected for each subject and stored in a zip-lock bag. Hairs will then be mounted on double stick tape on a microscope slide and stored at room temperature until LA-ICP-MS analyses (see below). Hair samples will also be logged-in and coded for identity protection in the P.I.'s laboratory.

Food and health diary. Subjects will be requested to keep a food diary for the periods spanning each of the 75 days of Trial 1 and 2. The diary is to include a list of types of food eaten and drinks consumed at each meal. Careful accounting of amounts of food or caloric intake will not be requested. In addition, subjects will be asked to record incidents of illness (e.g. cold or flu) or stresses (e.g. work or personal) that are likely to contribute to unusual eating patterns, digestive distress or metabolic imbalance. A food diary will not be requested for the intervening 4-month washout period. However, participants, at the visit prior to Trial 2, will be asked to comment on fish/seafood eating frequency and if illness or undue stress was experienced during the washout period.

Analytical procedures.

LA-ICP-MS of hair samples. Hair analyses will be done on individual strands of hair using LA-ICP-MS at the Dartmouth College Trace Element Analysis (TEA) Lab at Dartmouth College (<http://www.dartmouth.edu/~toxmetal/program-resources/trace-element-analysis/>). These measurements will be done by the TEA lab staff on a fee for service basis. Laser ablation will be carried out with a UP213 laser (ESI, Bozeman, MT) equipped with a programmable X-Y stage for predetermining coordinates for ablations of a series of spots on the hair shaft. Parameters of laser power, gas flow rates, dwell time and acquisition time will be optimized with [name] assistance. Methods of Hg determination will follow previously described protocols [10, 11]. Briefly, spots of 50 μ m will be ablated at 333 μ m intervals along a 3.0cm length of the initial segment of hair closest to the scalp. Hair growth occurs at approximately 1.1 cm per month. Therefore, 3.3cm of the initial segment of hair will be analyzed to cover the 75 days previous in which MeHg administration and elimination have occurred. The ^{202}Hg isotope will be detected and normalized to the amount of hair sampled in the ablation event by detecting ^{34}S in parallel and determining the Hg/S ratio. Quantification of Hg will be done by comparing Hg/S ratios to a matrix match hair sample [11].

Determination of MeHg elimination rate. Elimination rate will be determined from the normalized relative Hg concentrations in an individual hair strand over time, which is determined from the length of hair that grew over the interval from the last fish meal to the 60 day collection point. Growth rate of each individual hair will be calibrated by measuring the distance between the "peaks" of Hg observed in the hair resulting from the first and last fish meal, a period representing 14 days. Elimination rate will be determined by linear regression analysis of Hg concentration over time in a semi-log plot and expressed as $t_{1/2}$ in units of days.

Hg determinations in fecal samples. iHg and MeHg analysis and quantitation will be done in the URMC EHSC Elemental Analysis Lab. Analyses will employ a standard protocol of acid digestion followed by tetra-ethylborate (NaBET_4) derivatization and separation on GC-ICP-MS.

Data & Specimen Banking for Future Research Use. Samples (hair, feces)

will be stored in the P.I.'s laboratory until the analytical steps are completed. With subject consent, samples will be stored for future research purposes. Data emerging from the study will remain on the P.I.'s password protected personal computer.

Genetic/Genomic Research Activities

Genomic analysis will be carried out only on microbial samples from each subject. These studies are distinct from genomic testing of the subject's own DNA. Microbial genomic analyses will be done with a sequencing-based metagenomic method of identifying the presence and abundance of specific strains of bacteria. The relevance of the composition of the gut microbiota to MeHg toxicity will be explained to the subject. Recent focus on the gut microbiome has revealed several important roles for gut bacteria in health and disease. The subject will be made aware of the potential health benefits of management of gut microbiota composition and will have the opportunity to engage the P.I. in answering questions related to microbiome research.

Return of Individual Research Results

A summary of the study results will be shared with the participants upon request in a one-page electronic document. Participants will also be alerted to any public forum where study results will be presented and they are welcome to attend.

